10.1.6 Adverse Events

Adverse Events will be collected by the Investigator or qualified staff at the time points specified in Section 9.

10.1.7 Medical History

A full medical history will be conducted by the Investigator or qualified study staff at the time points specified in Section 9. Special attention will be paid to any fracture history.

10.1.8 Physical Examination

Physical examinations, full and brief, will be conducted at the time points specified in Section 9. Physical examinations will be performed by the Investigator or qualified study staff.

10.1.8.1 Full Physical Exam

Full physical examinations will include examination of general appearance, head, eyes, ears, nose, and throat (HEENT), heart, chest, abdomen, skin, lymph nodes, extremities, musculoskeletal, and neurological systems.

10.1.8.2 Brief Physical Exam

Brief physical examinations will include examination of general appearance, HEENT, heart, chest, abdomen, and skin.

10.1.9 Concomitant Medications and Therapies

The PI will encourage participants to maintain the medication and supplements they are on at enrollment through the course of the study. Subjects on aspirin or drugs that could affect coagulation will continue their medication as indicated. Several investigations show that preoperative aspirin ingestion and intravenous heparin therapy can be administered safely without concerns about the risk of postoperative bleeding and should not lead to modification or cessation of such therapy.

10.2 **Efficacy Assessments**

10.2.1 Functional Assessments

Details about how each assessment is performed is provided in the Clinical Evaluator Manual.

10.2.1.1 Bayley Scales of Infant Development

The Bayley Scales of Infant & Toddler Development – 3rd edition is a standardized, norm-reference assessment of infant and toddler development. It is intended for use between the ages of 1 to 2 months, inclusive (to be used only if age of enrollment is 1 to 36 months). It can also be used as a developmental checklist in older children with developmental delay, such as boys with Duchenne Muscular Dystrophy. It has five domains of development (cognitive, receptive and expressive communication and gross and fine motor).

10.2.1.2 North Star Ambulatory Assessment (NSAA)

The NSAA will be performed at the time points specified in Section 9. The NSAA is a clinician-administered scale that rates subject performance on various functional activities³¹. For subjects older than 3 years old, the NSAA will be administered as long as the subject remains ambulant.

During this assessment, subjects will be asked to perform 17 different functional activities, including a 10 m walk/run, rising from a sit to stand, standing on 1 leg, climbing a box step, descending a box step, rising from lying to sitting, rising from the floor, lifting the head, standing on heels, and jumping. Subjects will be graded as follows: 2 = achieves goal without any assistance; 1 = modified method but achieves goal independent of physical assistance from another person; and 0 = unable to achieve goal independently. A revised score is provided for children from 36 to 60 months.

10.2.1.3 100-Meter Walk / Run Test (100M)

The 100M will be performed at the time points specified in Section 9 starting at ages 3.5 years until nonambulant. In the 100-metre Walk/Run Time test the subject is asked to complete 4 laps on a 25 m track, for a total of 100 meters as quickly as safely possible. If the subject is able to run, he is encouraged to do so. The total time spent to complete the task is recorded.

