4 INTRODUCTION

4.1 Background of Duchenne Muscular Dystrophy

Duchenne muscular dystrophy (DMD) is a degenerative neuromuscular disease with an X linked recessive inheritance caused by mutations in the dystrophin gene, with a worldwide incidence of approximately 1 in 3500 newborn boys, irrespective of geographical region, race, or population density¹⁻³. The mutations that cause DMD typically disrupt the mRNA reading frame and prevent production of dystrophin, a critically important part of the protein complex that connects the cytoskeleton of a muscle fiber to the cell membrane and extracellular matrix. In the absence of dystrophin, the stress of repeated muscle contraction causes progressive muscle damage. The clinical effect of this disrupted dystrophin reading frame is progressive and ultimately fatal.

DMD is usually first diagnosed between the ages of 3 to 5 years⁴, when toddlers develop a waddling gait, lordosis, toe walking, calf hypertrophy, and a difficulty in climbing stairs. Over time, ambulation becomes increasingly abnormal. By 8 years of age, most subjects have lost the ability to rise from the floor and to climb stairs, show an increasingly labored gait, and often fall while walking, which leads to use of mobility devices such as strollers and scooters. Subjects with DMD walk slower than healthy boys and spend less time walking⁵ and they are significantly less active compared to healthy boys of similar age^{5, 6}. By 10 to 14 years of age, most are wheelchair dependent. Weakness of the arms and increasingly limited upper limb function, contractures, decubitus ulcers, and scoliosis (which often requires surgery), occur frequently. While pulmonary and cardiac functions are generally normal during early childhood, cardiac and diaphragmatic muscles progressively weaken during late childhood and adolescence leading to eventual dependence on ventilation support. Historically, subjects typically died from respiratory or cardiac failure in their late teens or early 20s^{7, 8}. Recent research suggests that use of ventilation support and steroids may increase life span by several years; however, DMD still has a mortality rate of 100%⁹. Corticosteroids used for palliative treatment of DMD can prolong ambulation and reduce the incidence of severe scoliosis; however, they are often associated with serious side effects^{10, 11} and are not always employed.

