Further, after 4 years on treatment in pivotal Study 201/202, subjects in the 30 mg/kg and 50 mg/kg eteplirsen cohorts experienced a decline on the six-minute walk test that was 165 meters less ($p=0.001$) than that observed in an external control group with comparable baseline characteristics that was identified using pre-defined filters of steroid use, age ≥ 7 and amenability to exon 51 skipping. Two of twelve eteplirsen-treated subjects lost ambulation versus 9 of 12 external control subjects.

Refer to the Investigator's Brochure for additional clinical data for eteplirsen.

Casimersen

Casimersen is being evaluated in 2 clinical studies:

- 4045-101²⁴ is a Phase 1, randomized, double-blind, placebo-controlled, dose-titration, safety, tolerability, and PK study in patients with DMD amenable to exon 45 skipping. The study is being conducted as a double-blind, placebo-controlled, dosetitration portion followed by an open-label extension.
- 4045-301²⁵ is a Phase 3, double-blind, placebo-controlled, multicenter study to evaluate the efficacy and safety of casimersen and golodirsen in patients with DMD who are amenable to skipping either exon 45 or 53, respectively.

No deaths or discontinuations from the study due to an adverse event (AE) have been reported. The majority of all TEAEs were nonserious, mild, and unrelated to study drug.

Refer to the Investigator's Brochure for additional clinical data for casimersen.

Golodirsen

Golodirsen is being evaluated in 2 clinical studies:

- 4053-101²⁶ is a Phase 1/2, randomized, double-blind, placebo-controlled, dose-titration, safety, tolerability, and pharmacokinetic (PK) study evaluating golodirsen in patients with advanced-stage DMD who are amenable to exon 53 skipping. The study is being conducted in 2 parts: Part 1 consists of a double-blind placebo-controlled, dose-titration and Part 2 is an open-label safety and efficacy evaluation.
- 4045-301²⁵ is a Phase 3, double-blind, placebo-controlled, multicenter study to evaluate the efficacy and safety of casimersen and golodirsen in patients with DMD who are amenable to skipping either exon 45 or 53, respectively.

No deaths or discontinuations from the study due to an AE have been reported. The majority of all TEAEs were nonserious, mild, and unrelated to study drug.

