5.3 Exploratory Objectives

Additional objectives are to evaluate the effect of casimersen, eteplirsen, or golodirsen analysing the changes from baseline to week 48 in the following:

- Functional abilities of subjects in comparison to the expected natural history using the following measures:
 - Subjects between 6 to 36 months of age at enrollment: Bayley Scales of Infant Development - Gross motor functions and fine motor functions.
 - Motor function as measured on the North Star Ambulatory Assessment (NSAA, ambulant boys age 3 years and older).
 - Ambulant subjects over age 3.5 years: endurance and muscle function as measured by the 100-Meter Walk / Run Test (100M)
 - ACTIVE-seated for boys over 5 years of age.
 - Forced vital capacity, as measured in absolute values and by % predicted forced vital capacity (FVC%) in patients aged ≥ 10 years
 - Peak expiratory flow as reported as % predicted by age and height (%PEF)
 - Timed functional tests for ambulant subjects 3 years or older:
 - time to complete 10-meter run
 - time to rise from the floor
 - time to climb 4 steps
 - time to descend 4 steps
- Pediatric Outcomes Data Collection Instrument (PODCI) for patients ages 2-17.
- Adult Patient-Reported Outcomes Measurement Information System (PROMIS) Upper Extremity Report for patients 18+ years.
- Immune staining may be performed on biopsy specimens for members of the dystrophin-associated protein complex, such as the sarcoglycans, dystroglycans and n-Nos.
- Muscle morphometrics may also be performed, including fiber size histograms and quantification of central nucleation.

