6.3.2 Efficacy Endpoints

6.3.2.1 Primary Efficacy Endpoint

The primary efficacy endpoint is:

- Change from Baseline to Week 48 in dystrophin expression quantified by western blot in muscle biopsy tissue.

6.3.2.2 *Secondary Efficacy Endpoints*

Secondary efficacy endpoints are:

- Change from Baseline to Week 48 in expression of dystrophin as measured by immunofluorescent signal intensity and percent dystrophin positive fibers (PDPF) in muscle tissue sections in comparison to baseline values.
- The efficiency of splicing alteration will be measured by RNA Sequencing (RNA-Seq) to establish DMD mRNA copy number and the exon-exon junction frequency quantified, with normalization to exon junction read values from an exon junction in regions distinct from the targeted exon.

6.3.2.3 *Exploratory Efficacy Endpoints*

Exploratory efficacy endpoints are based on the change from Baseline to Week 48 in the following measures:

- Subjects 6 to 36 months of age at enrollment: Change from baseline in scores on the Bayley Scales of Infant Development – gross motor functions and fine motor functions.
- Change from Baseline to Week 48 in NSAA (subjects 3 years or greater).
- Change from Baseline to Week 48 on the 100M in ambulant subjects over the age of 3.5 years.
- Change from Baseline to Week 48 in ACTIVE-seated for boys over 5 years of age.
- Changes in FVC and FVC% predicted in patients aged ≥ 10 years.
- Peak expiratory flow as reported as % predicted by age and height (%PEF).
- Timed functional tests for ambulant subjects 3 years or older:
 - time to complete 10-meter run
 - time to rise from the floor
 - time to climb 4 steps
 - time to descend 4 steps
- Pediatric Outcomes Data Collection Instrument (PODCI) for patients ages 2-17.
- Adult Patient-Reported Outcomes Measurement Information System (PROMIS) Upper Extremity Report for patients 18+ years.
- Immune staining may be performed on biopsy specimens for members of the dystrophin-associated protein complex, such as the sarcoglycans, dystroglycans and n-Nos.
- Muscle morphometrics may also be performed, including fiber size histograms and quantification of central nucleation.

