14.1 General Considerations

This section describes the rules, conventions, statistical analysis, and presentation of data for this study.

All available data will be included in data listings and tabulations. No imputation of values for missing data will be performed. Percentages of subjects with AEs or laboratory abnormalities will be based on non-missing values.

All data collected in this study will be presented using summary tables and subject data listings. Summary statistics for raw and change from Baseline data of continuous variables will minimally include n, mean, standard deviation (SD), minimum, median, and maximum. For categorical variables, frequencies and percentages will be presented. Graphical displays will be provided as appropriate.

Endpoints will be assessed primarily using simple descriptive statistics and/or inferential statistics. Baseline will generally be defined as the last available value before dosing.

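### A boy who loses a walking ability during the 48 weeks drops out of the Week 48 functional change scores because of his outcome, and no planned summary counts the loss

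*Combined protocol and SAP*

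**What the plan says.** All references are to the combined protocol and SAP.

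- **NSAA** (Section 10.2.1.2): "the NSAA will be administered as long as the subject remains ambulant".
- **100M** (Section 10.2.1.3): "starting at ages 3.5 years until nonambulant". The result is the time to complete the course.
- **Timed tests** (Sections 5.3 and 6.3.2.3): "Timed functional tests for ambulant subjects 3 years or older". Section 10.2.1.6 gives only the age limit, but what is recorded is again a time.
- **Missing data** (Section 14.1): "No imputation of values for missing data will be performed".
- **Endpoint** (Section 6.3.2.3), for example: "Change from Baseline to Week 48 in NSAA (subjects 3 years or greater"). Loss of ambulation, of rising from the floor or of stair climbing is not on the list.
- **Purpose** (Section 5.3): "Functional abilities of subjects in comparison to the expected natural history using the following measures".
- **Analysis** (Section 14.3.1.3): listings and descriptive summaries are optional. No natural-history cohort or method of comparison is named.

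Section 14 gives no score, zero speed or category for a boy who loses an ability after Baseline.

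**The concern.** The missingness is caused by the outcome. A boy who stops walking has no Week 48 NSAA or 100M. A boy who still walks but can no longer rise or climb has no time for that task. A mean over the remaining boys describes only those who kept the ability.

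The event is within the protocol's own picture of the disease. Section 4.1 states: "By 8 years of age, most subjects have lost the ability to rise from the floor and to climb stairs", and puts wheelchair dependence for most at 10 to 14 years. Section 7.2 sets neither an upper age limit nor an ambulation requirement. Section 4.3 cites loss of ambulation as evidence for eteplirsen, yet this study would not tabulate it.

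Nothing else in the plan catches it reliably. Disease progression is an adverse event only at the investigator's discretion (Section 11.3.3). Under the visit lists in Section 9, ACTIVE-seated is for non-ambulant boys only, so a boy who stops walking on study would have no Baseline value for it either.

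At stake is how the functional results of an uncontrolled study of six boys are read against natural history.

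**Working it through.** **Plan's own figures.** The documents give none for function. Their only computed design figures are the smallest two-sided p values for the western blot test: 2/2^5 = 0.0625 and 2/2^6 = 0.03125. Both reproduce, and neither bears on this point.

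**Step 1: how often might it happen?** Section 4.3 gives a frequency after 4 years: "Two of twelve eteplirsen-treated subjects lost ambulation versus 9 of 12 external control subjects". Assume a constant yearly rate:

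- treated: 1 - (10/12)^(1/4) = 0.045
- external control: 1 - (3/12)^(1/4) = 0.293

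The chance that at least one of m ambulant boys loses ambulation in about a year is 1 - (1 - p)^m:

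| m | p = 0.045 | p = 0.293 |
|---|---|---|
| 2 | 9% | 50% |
| 4 | 17% | 75% |
| 6 | 24% | 88% |

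These rates come from boys amenable to exon 51 skipping (treated 7 to 13 years, controls 7 or over). They would be lower in younger boys. The documents give no rate for losing rise or climb alone.

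**Step 2: NSAA.** The scale has 17 items graded 0 to 2, so at most 34 points. Let k of m ambulant boys lose ambulation from mean baseline b, let the others change by o on average, and let a lost boy keep s points had he been tested. Then

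observed mean - full mean = (k/m) × (o + b - s).

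Assumed ranges: k = 1, m = 4 or 6, b = 5 to 15, o = 0 to -6. With s = 0:

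| m | b | o | Full mean | Shift |
|---|---|---|---|---|
| 6 | 10 | 0 | -1.67 | +1.67 |
| 6 | 10 | -6 | -6.67 | +0.67 |
| 4 | 10 | 0 | -2.50 | +2.50 |
| 4 | 10 | -6 | -7.00 | +1.00 |
| 4 | 15 | 0 | -3.75 | +3.75 |
| 4 | 5 | -6 | -5.75 | -0.25 |
| 6 | 5 | -6 | -5.83 | -0.17 |

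The shift is upward unless the lost boy started so low that he could lose fewer points than the others lost. Retained points shrink it. For m = 6, b = 10, o = -2, the shift is (1/6)(8) = +1.33 with s = 0, and (1/6)(6) = +1.00 to (1/6)(4) = +0.67 with s = 2 to 4 (assumed).

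**Step 3: 100M as speed, lost boy = 0 m/s.** The shift is (1/m) × (o + v). Assume baseline speed v = 1.0 to 1.5 m/s for the lost boy and mean change o = 0 to -0.2 m/s in the others:

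- m = 6: 0.8/6 = +0.13 to 1.5/6 = +0.25 m/s
- m = 4: 0.8/4 = +0.20 to 1.5/4 = +0.38 m/s

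It is upward throughout this range.

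**Step 4: rise time.** Assume four boys at 4, 6, 9 and 14 s who become 4.5, 7, 11 s and unable. Under the plan, n = 3 and the mean change is (0.5 + 1 + 2)/3 = +1.17 s. The boy who can no longer rise contributes nothing. As 1/time, the mean change is -0.024 per second for the three and -0.036 per second for all four, with unable = 0.

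**Step 5: ACTIVE-seated.** Sections 5.3 and 6.3.2.3 give it to boys over 5, and Section 10.2.1.4 to those 5 and older, without regard to ambulation. The lists in Sections 9.1.2.2, 9.1.3.1, 9.5, 9.7 and 9.8.1 restrict it to non-ambulant boys. Only the first reading supplies a Baseline value for a boy who loses ambulation later.

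**The case against.** The other side has several fair points.

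- **Nothing may happen.** Section 4.1 describes milestones over years, and the study lasts 48 weeks. Boys may be very young or already non-ambulant at entry. A boy who could not rise or climb at Baseline had no change score to lose. This stands: the bias is conditional.
- **The loss would be visible.** Section 14.1 puts all available data in listings and n beside every summary, and six profiles can be read by eye. This limits the harm, but a smaller n does not say why a value is missing.
- **No natural-history estimate is planned.** Section 5.3 states the aim, but Section 14.3.1.3 offers only optional description. This also stands.
- **Inability may already be recorded.** Section 10.2.1 defers test conduct to the Clinical Evaluator Manual, which is not available here. Even so, Section 14 has no rule for using such a record.
- **NSAA zero is a grade for one item.** A reader might infer that the scale already assigns 0 to a non-ambulant boy. It does not. Items such as head lifting may still be achieved, so a total of 0 for an untested boy is a worst-case assignment, not an observed score.

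**Conclusion.** The point holds in limited form. Following the stated rules removes any boy who loses an ability on study from the Week 48 change scores, because of that loss. If it occurs, mean changes in the 100M and timed tests are likely to look too favourable. For the NSAA total that is usual but not certain. One loss can move a mean materially, as the working shows. Those sizes rest on assumed baselines, declines and numbers of ambulant boys, and the likelihood on a constant rate borrowed from other cohorts.

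A reader might infer that the comparison with natural history is biased towards benefit. The documents do not support that: no such comparison is specified, and its direction would depend on how the comparison cohort handles lost ambulation. With the same truncation there, the bias could shrink or reverse. Nor does the point touch the primary or secondary endpoints, which rest on biopsy tissue. This is a cheap improvement of low severity.

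**What to change.** In Sections 6.3.2.3 and 14.3.1.3:

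1. Report, as an exploratory outcome and beside every functional mean, how many boys with the ability at Baseline lost ambulation, rise from floor or stair climb by Week 48.
2. Record inability explicitly for the 100M and timed tests. Also summarise them as speed (distance/time or 1/time) with inability as 0, and keep seconds in the listings.
3. For the NSAA, show the observed-case summary together with a worst-case summary that assigns 0 to boys who lost ambulation, labelled as an assignment.
4. Apply the same rules to any natural-history data used for comparison.
5. Reconcile Sections 5.3, 6.3.2.3 and 10.2.1.4 with the Section 9 visit lists on who receives ACTIVE-seated.

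The cost is wording, a CRF field if none exists, and a little more analysis. Items 1 to 4 need no new assessment. The downsides are somewhat less favourable means and less familiar units.

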10.2.1.4 ACTIVE-Seated Test

The ACTIVE-Seated Test will be performed at the time points specified in Section 9 for subjects 5 years and older.

10.2.1.5 Pulmonary Functional Testing (PFT):

The PFT will be performed at the time points specified in Section 9 in subjects 10 years and older. The PFT involves assessing maximal lung function with both a spirometer and respiratory pressure meter. The Forced Vital Capacity (FVC) is reported on the subject's CRF.

10.2.1.6 Timed Functional Test

Timed functional tests will be conducted in subjects 3 years and older.

10.2.1.6.1 Time 4-Step Test

The Timed 4-Step Test will be performed at the time points specified in Section 9. Timed 4-stair climb quantifies the time required for the patient to ascend and descend four standard stairs (6" height for each step).

10.2.1.6.2 10-meter Walk Run (10MWR)

The 10MWR will be performed at the time points specified in Section 9. The time it takes the subject to move will be recorded.

10.2.1.6.3 Rise Time

Rise Time will be recorded at the time points specified in Section 9. The time it takes the subject to rise from supine will be recorded.

10.2.2 Quality of Life Assessment: PODCI

Quality of life will be evaluated for subjects at the time points specified in Section 9 using the PODCI, a parent-reported measure of quality of life for children with acute or chronic illnesses. The PODCI has been used to evaluate health-related quality of life in subjects with *DMD*^{32, 33}. The 86-item instrument generates 8 scales including upper extremity and physical function scale, transfer and basic mobility scale, sports/physical functioning scale, pain/comfort scale, treatment expectations scale, happiness scale, satisfaction with symptoms scale, and global functioning scale^{32, 34}.

10.2.3 Quality of Life Assessment: PROMIS

The Patient-Reported Outcomes Measurement Information System (PROMIS) is a collection of patient-reported measures assessing various domains of physical, mental, and social health. PROMIS tools were developed in collaboration with NIH and are considered psychometrically-sound instruments created to be relevant across conditions and symptoms. The PROMIS Upper Extremity questionnaire assesses self-reported performance of 16 upper extremity tasks with higher scores indicating higher function with a maximum score of 80 points.

